4.1 Study outcomes

4.1.1 Baseline characteristics

Baseline characteristics will be collected following subject enrollment into the study, and will be based on physical examination and medical history. A complete list of baseline characteristics is shown in Table 2.

Table 2. Baseline characteristics

Measure Type	Description
Demographics	Age (in years) Gender Race Employment status Location subject presents from (e.g. from home, LTC, SNF, nursing home)
Comorbidities	Myocardial infarction Congestive heart failure Peripheral vascular disease Cerebrovascular disease Dementia Chronic pulmonary disease Rheumatologic disease Peptic ulcer disease Mild liver disease Diabetes without complications Diabetes with complications Renal disease Moderate or severe liver disease (Child-Pugh Class B and C) Any malignancy, including leukemia and lymphoma Metastatic solid tumor If subject has cancer, whether active vs. remitted/cured Alcohol/drug abuse/illicit needle use Malnutrition HIV

Measure Type	Description
	Immunocompromising conditions other than HIV Altered mental status
Charlson Comorbidity Index ^b (CCI)	Derived variable based on recorded comorbidities: Calculation of the CCI for each subject at baseline to assess the risk of 1 year mortality
Infection type	Cellulitis/erysipelas, wound infection, or major cutaneous abscess
Infection characteristics	Lesion size (as described in Appendix A) and location Thrombocytopenia (<150,000 platelet count or site-specific definition) Hyperglycemia (>120mg/dL blood glucose or site-specific definition) Hyponatremia (<135 mEq/L blood sodium or site-specific definition) Acidosis (<7.35 pH of the blood or site-specific definition or described in medical chart) Uremia (as described in medical chart) Anemia (14-18 g/dL hemoglobin for men or 12-16 g/dL hemoglobin for women or site-specific definition) Fever (>98.6 degrees Fahrenheit or site-specific definition) SIRS criteria ^c at enrollment, including highest or lowest recorded RR and highest or lowest recorded BPM/highest or lowest recorded fever/highest or lowest WBC count or amount of immature cells Highest or lowest recorded BP at enrollment Laboratory results at baseline and during follow-up (e.g. Total white blood cell count, hemoglobin, sodium, glucose, serum creatinine, and C-reactive protein)

^b Deyo et al 1992

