4.0 Study Measures

4.1 Baseline Characteristics

The following baseline characteristics will be collected:

- **Demographic data:** Age (in years, derived and described in Appendix B), gender, ethnicity, race, employment status, and location patient presents from (e.g. from home, long-term care [LTC], skilled nursing facility [SNF], nursing home).
- **Comorbidities:** myocardial infarction, congestive heart failure, peripheral vascular disease, cerebrovascular disease, dementia, chronic pulmonary disease, rheumatologic disease, peptic ulcer disease, mild liver disease, diabetes with/without complications, renal disease, moderate or severe liver disease (Child-Pugh Class B and C), any malignancy (including leukemia and lymphoma), metastatic solid tumor, cancer (active, remitted/cured), alcohol/drug abuse/illicit needle use, malnutrition, human immunodeficiency virus (HIV), other immunocompromising conditions, altered mental status, lymphedema or chronic venous stasis, and peripheral vascular disease.
- **Charlson Comorbidity Index (CCI):** A derived variable based on the presence/absence of the comorbidities specified above. The formula by which the CCI is calculated is detailed in Appendix C.
- **Infection type:** Cellulitis/erysipelas, wound infection, major cutaneous abscess
- **Infection and clinical characteristics during the initial assessment at the hospital and end of treatment visit:**
 - Lesion size and location
 - Pain and tenderness associated with the lesion
 - Fever ($>100.4^{\circ}\text{F}$; $>38.0^{\circ}\text{C}$; or site-specific definition)
 - *Systemic inflammatory response syndrome* (SIRS) (see Appendix B)
 - Blood pressure (BP, in mmHg)
 - Total white blood cell count ($\times 10^9/\text{L}$)
 - Hemoglobin (g/dL)
 - Sodium (mmol/L)
 - Glucose (mg/dL)
 - Serum creatinine (mg/dL)
 - C-reactive protein (mg/dL)
 - Rapid microbial assay
 - Microbiological culture type (i.e. blood, wound swab, urine) and results thereof
 - Presence of recurrent infection and/or any ABSSSI infections in the prior 6 months
- **Utilization of healthcare services in prior 3 months:** Hospitalizations and primary reason, surgical interventions and primary

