6.2.2 Demographic and Baseline Characteristics

All demographic data will be summarized in tables and listings for the enrolled and FAS populations. Descriptive statistics will be summarized for age (in years), height at baseline (in cm), weight at baseline (in kg) and body mass index (BMI) at baseline (in kg/m²). Patient counts and percentages will be summarized for age (e.g., <20 years, 20-29 years, 30-39 years, etc.), race/ethnicity, gender, employment status (e.g., employed, full time, part time, unemployed), admission source (e.g., from home, LTC, SNF, nursing home), and insurance information. This information will be captured in listings with date of birth.

All baseline characteristics for comorbid conditions will be summarized for the FAS population by patient counts and percentages in tables and include the following measures: myocardial infarction, congestive heart failure, peripheral vascular disease, cerebrovascular disease, dementia, chronic obstructive pulmonary disease, connective tissue disease, peptic ulcer disease, mild liver disease, moderate or severe liver disease (Child- Pugh Class B and C), hemiplegia, lymphedema / chronic venous stasis, diabetes mellitus (with and without end-organ damage), moderate to severe chronic kidney disease (e.g., actual measurement and GFR, estimated measurement and GFR, unknown measurement), leukemia and remission status, lymphoma and remission status, metastatic solid tumor and remission status, alcohol abuse, drug abuse including illicit needle use, protein calorie malnutrition, immuno-compromising conditions such as HIV, acquired immune deficiency syndrome (AIDS), receiving ≥20 mg Prednisone daily (or therapeutically equivalent steroid), receiving TNF inhibitors, receiving any other immune modulating medication including biologics, and receiving chemotherapy. The Charlson Comorbidity

Index will be derived and described by descriptive statistics. All data will be reflected in listings.

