6.2.4 Outcomes

6.2.4.1 Primary Outcomes

Primary Outcome: Infection-related Total Admitted Hospital Days

Infection-related total admitted hospital days will be calculated by two methods for the FAS population. First, LOS will be calculated by inpatient only stays and second, LOS will be calculated by inpatient stays including time spent in prolonged observation status (> 1 day). Descriptive statistics for the primary

[REDACTED]

outcome will be shown in a table by initial care, follow-up, and overall for the pre-period and post-period, and depicted graphically overall using box plots. Patient counts and percentages will be given for the primary outcome (e.g., 0 day, 1 day ... > 5 days). Descriptive statistics in the table will be repeated by all patients and patients who complete the study for comparison.

The primary analysis will consist of Hypothesis testing using a two sided (two sample equal-variance) t-test, with a significance level of 0.05, comparing the difference in total time (in days) spent in hospital between the pre- and post-periods. Violations of assumptions for the t-test in the data will be checked for. An appropriate alternative method will be selected if a major violation to an assumption is present, such as the Mann-Whitney U test². Overall differences in descriptive statistics between the pre- and post-periods for infection-related total admitted hospital days will be reported.

Because the baseline characteristics of the pre-period may differ from those of the post-period, a secondary analysis using a multivariate regression analyses, specifically a generalized linear mixed model (GLMM), [REDACTED]. As the outcome is expected to be heavily right skewed, the number of hospital days will be modeled assuming a negative binomial distribution with log link. If the model does not converge or fit, an alternate distribution will be selected. This model will assume mutual independence between the sites. Similar to above, the multivariate analysis will be completed for the primary outcome for inpatient stays only as well as including time spent under observation, as well as for all patients and patients who complete the study for comparison.

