Clinically relevant baseline characteristics of interest for the adjusted analysis (as described in Section 4.1) including the following variables: age, gender (Male, Female), race (White/Caucasian, Black or African American, Other), employment status (Full-Time, Part-Time, None), insurance plan type (Private commercial plan, Government funded, Uninsured, Other), Charlson Comorbidity Index, lesion surface area (<75cm cm², =>75 cm² - 150 cm², >150 cm²), infection type (Wound infection, Cellulitis/erysipelas, Abscess), prior health resource use (Yes, No, Unknown), prior antibiotic treatment failure (Yes, No, Unknown), presence of SIRS criteria (<2 or >=2), presence of recurrent infection in prior 6 months (Yes, No, Unknown), any health resource use in prior 3 months (Yes, No, Unknown), as well as is patient was immunocompromised (Yes, No, Unknown). Patients will be defined as immunocompromised if they have evidence of any of the following at baseline: Connective tissue disease, diabetes mellitus, leukemia, or malignant lymphoma. These characteristics will be selected for the GLMM model by use of stepwise selection with the [REDACTED] procedure and a statistical significance level of <0.1. Categorical variables will be collapsed where possible. The primary predictor variable will be a pre/post-period indicator, and potentially other selected characteristics will be forced into the model based on clinical rationale and distributions observed in the data (specifically

imbalance between the pre- and post-periods); as it is assumed that patients enrolled in each site will be correlated, a generalized linear mixed model (GLMM) will be generated. The GLMM will adjust for correlated data among patients at sites by using a RANDOM statement in analyses. The Kenward and Roger method for approximating degrees of freedom will be taken for inference on the fixed effects. The final model results will be presented in a table.

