9.0 Appendices

Appendix B: Derived Variables

[figure not shown]
Analysis Section (Visit)	Variable (Units)	Definition
General (Baseline)	Enrollment date	Informed consent date
General (Baseline)	Baseline date	Hospital admission date at initial episode of care
General (Initial Care)	Initial care indicator	If enrollment date \leq date \leq enrollment date + 13 days then = Yes Else = No
General (Follow-up)	Follow-up indicator	If enrollment date + 14 \leq date \leq enrollment date + 43 days then = Yes Else = No
Demographics (Baseline)	Age (years)	Round down to nearest integer((Initial hospital admission date - date of birth + 1)/365.25), when both dates are available.
Demographics (Baseline)	BMI	weight (kg)/ [height(m)] ² Where necessary, height and weight will be converted to proper units.
Infection Characteristics (Baseline)	CCI	Will be scored as described in Appendix C. Includes variables for raw score and 10 year survival probability.
Infection Characteristics (Baseline)	Immunocompromised	=YES if any of the following at baseline: 
 - Diabetes mellitus - Leukemia - Malignant lymphoma
Infection Characteristics (Baseline)	Fever	If temperature > 38 ° C then =Yes Else =No
Infection Characteristics (Baseline)	SIRS Criteria Met	SIRS criteria include abnormalities in temperature, heart rate, respiration, and white blood cell count. Specifically included are:

[figure not shown]
Analysis Section (Visit)	Variable (Units)	Definition
		
 • Fever of more than > 38.0°C or hypothermia with temperature < 36.0°C • Tachycardia with heart rate > 90 beats/minute or • Tachypnea with respiratory rate of > 20 breaths/minute or PaCO₂ of less than 32mmHg • Abnormal white blood cell count: leukocytosis >12,000/microliter, leucopenia <4,000/microliter, or >10% immature cells (bands).^{3,4} 
If 2 or more criteria present = Yes Else = No

Antibiotic Medications (Initial Care and Follow-up)	Days Received Antibiotic Medication	Σ (Medication end date – Medication start date +1), when both dates are available. If dates overlap (e.g., end date and next start date are identical) then subtract 1 from summation for each occurrence.

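### The SAP defines the immunocompromised covariate for the adjusted model in two ways, and neither uses the conditions that SAP 6.2.2 groups as immunocompromising

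*SAP*

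**What the plan says.** SAP 6.2.4.1 makes the unadjusted two-sample t-test the primary analysis. Because the two periods may differ at baseline, it adds "a secondary analysis using a multivariate regression analyses": a negative binomial generalized linear mixed model. Fourteen candidate covariates are listed, to be chosen stepwise at a significance level below 0.1. Other characteristics may be forced in on clinical grounds or because of observed imbalance. One candidate is whether the patient was immunocompromised (Yes, No, Unknown), which is Yes on baseline evidence of "Connective tissue disease, diabetes mellitus, leukemia, or malignant lymphoma".

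SAP Appendix B derives the same variable as "YES if any of the following at baseline", followed by diabetes mellitus, leukemia and malignant lymphoma. Connective tissue disease does not appear.

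SAP 6.2.2, which sets out the baseline tables, names a separate group: "immuno-compromising conditions such as HIV, acquired immune deficiency syndrome (AIDS), receiving ≥20 mg Prednisone daily (or therapeutically equivalent steroid), receiving TNF inhibitors", then "receiving any other immune modulating medication including biologics, and receiving chemotherapy". Connective tissue disease, diabetes, leukemia and lymphoma stand earlier in the same sentence as comorbidities in their own right.

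The items are planned for collection. SAP 4.1 lists "human immunodeficiency virus (HIV), other immunocompromising conditions, altered mental status" among the comorbidities, and Protocol 4.1.1, Table 2, has HIV and "Immunocompromising conditions other than HIV" as separate entries.

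**The concern.** This is a non-randomised comparison of two periods, and the adjusted model is the SAP's stated regression answer to differences in case mix. The flag is the only candidate covariate labelled as immune status. If it leaves out the conditions that the SAP itself tabulates under that name, a shift between periods in HIV, steroid, biologic or chemotherapy use would not show in it. The report could still say that immune status had been considered.

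The two definitions add a separate problem. The covariate has to pass a stepwise threshold, so whether it enters the model could depend on which section the programmer follows. Nothing in the SAP says which section governs.

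**Working it through.** **No figure in the plan depends on this variable.** The sample size (SAP 6.1.2) uses a 2-day difference, SD 3.0 days, two-sided alpha 0.05 and 80% power. The normal approximation gives 2 × (1.960 + 0.842)² × 3.0² / 2² = 35.3, or 36 per period. The exact t-test gives 36.3, or 37 per period, as stated. No covariate enters that calculation.

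**Set comparison.** The 6.2.2 group has six members: HIV, AIDS, prednisone ≥20 mg daily or equivalent, TNF inhibitors, other immune modulators including biologics, and chemotherapy.

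- Members of the group in the 6.2.4.1 definition (four conditions): 0 of 6.
- Members of the group in the Appendix B definition (three conditions): 0 of 6.
- Difference between the two definitions: one condition, connective tissue disease.

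| Patient whose only relevant condition is | In the 6.2.2 group | 6.2.4.1 | Appendix B |
|---|---|---|---|
| HIV | Yes | No | No |
| TNF inhibitor use | Yes | No | No |
| Chemotherapy for a solid tumor | Yes | No | No |
| Connective tissue disease | No | Yes | No |
| Diabetes | No | Yes | Yes |
| Leukemia or lymphoma | No | Yes | Yes |

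**Scale, by assumption only.** The documents give no prevalences. Assume diabetes 10–40%, connective tissue disease 1–10%, leukemia and lymphoma 0.5–3% each, and any 6.2.2 condition 5–15%, all independent, with 86 enrolled.

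Patients coded differently by the two definitions = 86 × p(connective tissue disease) × (1 − p(diabetes)) × (1 − p(leukemia)) × (1 − p(lymphoma)). With leukemia and lymphoma at 1% each:

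- Low: 86 × 0.01 × 0.60 × 0.99 × 0.99 = 0.5.
- High: 86 × 0.10 × 0.90 × 0.99 × 0.99 = 7.6.

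Patients with a 6.2.2 condition but coded No = 86 × q × (1 − f), where q is the prevalence of any 6.2.2 condition and f is the proportion flagged:

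- Low (6.2.4.1 definition): f = 1 − 0.60 × 0.90 × 0.97 × 0.97 = 0.492, and 86 × 0.05 × 0.508 = 2.2.
- High (Appendix B definition): f = 1 − 0.90 × 0.995 × 0.995 = 0.109, and 86 × 0.15 × 0.891 = 11.5.

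These counts show what the assumptions imply and are not estimates. Independence is doubtful, since chemotherapy goes with leukemia and lymphoma, and steroids or TNF inhibitors with connective tissue disease. Such overlap would lower the second count. If the 6.2.2 conditions are excluded at enrolment, that count is zero.

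**The case against.** Several points on the other side carry weight.

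- **Limited reach.** The flag is one of fourteen stepwise candidates in a secondary analysis and may never enter the model. This stands, and it sets the severity.
- **Other routes to adjustment.** The Charlson index is also a candidate and is derived from a comorbidity list that includes HIV (SAP 4.1; the scoring appendix is not visible). SAP 6.2 compares comorbid conditions between periods, and 6.2.4.1 allows characteristics to be forced in. A reader might infer that the model cannot adjust for immune status at all. The documents do not support that: these routes exist, and leukemia, lymphoma and connective tissue disease carry some immune information. But the forcing rule is unspecified and depends on the data, so it does not replace a correct definition.
- **A diabetes flag?** A reader might infer that the variable is in effect an indicator of diabetes. That needs prevalences which the documents lack. Under the ranges above, patients with diabetes make up 42% to 97% of those flagged by the 6.2.4.1 definition, so the claim is possible but not established. Nor can it be said that the flag finds immunocompromised patients only at chance level, because that result follows by algebra from assuming independence.
- **Redacted exclusions.** Most exclusion criteria in Protocol 3.4.2 are blacked out and may remove some or all of these patients. That SAP 6.2.2 tabulates the conditions does not prove they can be enrolled: it also tabulates hemiplegia, which Protocol 3.4.2 gives as an example of an excluded neurological disorder. This stands as a limit on size. If such patients are absent, the variable is still misnamed.
- **Possible text loss.** Appendix B is a table, and its three items match the last three in 6.2.4.1, so a lost first item cannot be ruled out. The page should be checked. The omission of the 6.2.2 conditions does not depend on this.
- **Clinical judgement.** The 6.2.2 list is worded as examples, and 6.2.4.1 is free to call its own four conditions immunocompromising. That is fair, but the SAP gives no reason for using one meaning in the tables and another in the model.

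**Conclusion.** The concern holds as an error of definition. The SAP states two non-identical rules for one covariate, subject to checking the Appendix B page, and neither rule uses any of the six conditions that 6.2.2 groups as immunocompromising. As written, the flag misclassifies immune status by the SAP's own description, adjusts for it poorly, and can code the same patient differently.

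The number of patients affected is unknown. The illustrative ranges (about 0.5 to 8 of 86 coded differently, and about 2 to 11.5 of 86 with a listed condition coded No) rest wholly on assumed independent prevalences, and the second could be zero if redacted exclusions apply. The effect is confined to a candidate covariate in the secondary adjusted model. The primary t-test, its significance level and the sample size do not change. Severity is minor.

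**What to change.** Put one definition in both SAP 6.2.4.1 and Appendix B: Yes if the patient has any condition in the 6.2.2 group (HIV, AIDS, prednisone ≥20 mg daily or equivalent, TNF inhibitor, other immune-modulating drug or biologic, chemotherapy), or leukemia or lymphoma. State in Appendix B how No and Unknown are assigned, since 6.2.4.1 allows for both. Carry diabetes, and connective tissue disease if wanted, as separate candidates or leave them to the Charlson index.

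If the full exclusion criteria keep these patients out, keep a single reconciled list and rename the variable for what it contains, so that the report does not claim adjustment for immune status.

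The cost is SAP wording and a small programming change on items already planned for collection. The downside is that the covariate may be sparse: at an assumed 5–15%, the 6.2.2 conditions would cover about 4 to 13 of 86 patients (86 × 0.05 = 4.3; 86 × 0.15 = 12.9), so its coefficient may be imprecise.

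### The secondary adjusted model of hospital days selects covariates by stepwise p<0.1 with no visible allowance for it in the confidence interval, and its site random effect cannot be estimated in a one-site trial

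*SAP*

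**What the plan says.** The primary analysis of infection-related hospital days is an unadjusted two-sample t-test. SAP 6.2.4.1 adds a secondary, adjusted analysis and gives the reason: "Because the baseline characteristics of the pre-period may differ from those of the post-period". It is a negative binomial mixed model with log link.

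- **Selection.** From a list of baseline variables, "These characteristics will be selected for the GLMM model by use of stepwise selection", at a level below 0.1. The procedure name is redacted.
- **Forcing.** Besides the period indicator, "potentially other selected characteristics will be forced into the model based on clinical rationale and distributions observed in the data", with imbalance between periods given as the particular case. No threshold is stated.
- **Fits.** The model is run for two length-of-stay definitions, "as well as for all patients and patients who complete the study for comparison", which makes four fits. Of the output the SAP says only: "The final model results will be presented in a table".
- **Site.** "The GLMM will adjust for correlated data among patients at sites by using a RANDOM statement in analyses", and also "This model will assume mutual independence between the sites". Inference on fixed effects uses Kenward-Roger.
- **Fallback.** "If the model does not converge or fit, an alternate distribution will be selected".

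SAP 6.1.2 expects 86 patients at one US site, and the protocol synopsis names one site.

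**The concern.** The two periods are not randomised groups, so a difference in hospital days can reflect case mix. In the visible text this model is the analysis of the primary outcome that addresses case mix, and readers will look to it to judge whether a period effect survives adjustment.

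Stepwise selection keeps the covariates that happen to fit these data and drops the rest. The refitted model then reports an SE as though the retained set had been known beforehand, so the interval is too narrow. No visible text allows for this, although part of the sentence introducing the model is redacted. If selection is rerun in each of the four fits, the all-patients and completers results may also differ merely because their covariates differ.

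The site term is a separate matter: one site gives no information on variation between sites.

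**Working it through.** **Inputs.** From SAP 6.1.2: 43 patients per period, one site, mean stay 4.0 days, SD 3.0, planned reduction 2 days, two-sided 0.05, 80% power. From SAP 6.2.4.1: the candidate list, p<0.1, negative binomial with log link.

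**The plan's own figure.** 2 × (1.960 + 0.842)² × 3² / 2² = 35.3, so 36 per period by the normal approximation. The t-based calculation gives 36.3, so 37, as stated. The plan gives no SE or error rate for the adjusted model, so there is none to reproduce.

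**Candidates against patients.** Health resource use appears twice, once without a time window and once for three months; SAP 4.1 collects only the three-month window, so I count it once. Degrees of freedom: age 1, gender 1, race 2, employment 2, insurance 3, Charlson index 1, lesion area 2, infection type 2, resource use 1, prior antibiotic failure 1, SIRS 1, recurrence 1, immunocompromised 1 = 19. With four Unknown levels kept, 23. Patients per df: 86/19 = 4.5 and 86/23 = 3.7.

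**Simulations.** The SAP's mean and SD imply dispersion (9 − 4)/16 = 0.3125. Three sets were run with 43 + 43 patients. Shortfall means 1 − (mean reported SE)/(actual SD of the estimate).

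- Set A: 2,000 trials in each of seven scenarios; 14 candidates (20 df); none, four weak or four moderate prognostic covariates; some scenarios with period imbalance; rate ratio 1 or 0.5.
- Set B: 1,600 trials in each of four scenarios; 13 candidates; no period effect; moment dispersion; t on residual df. Assumed log-rate effects were 0.12 to 0.25. Scenarios: (a) no imbalance, (b) and (c) imbalanced confounders all inside the example list of eight given under the fix, (d) two of four confounders outside it.
- Set C: about 1,900 to 2,200 trials per scenario; assumptions and inference like set B.

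| Rule (period kept in) | Set A: shortfall; error | Set B | Set C |
|---|---|---|---|
| Stepwise p<0.1 | 12.0-16.3%, or 10.6-13.1% after residual-df scaling; 8.0-11.1% | 11-16%; 7.6-10.9% | 11%; 8.2-8.8% |
| Stepwise plus forcing at pre/post p<0.1 | not run | 7-9%; 6.3-7.1% | 5-9%; 5.8-7.8% |
| Fixed list of eight | not run | −1 to 4%; 4.8-7.1% | −1 to 3%; 4.6-6.1% |
| All candidates fixed | 1.3-6.2% scaled; 5.0-6.5% | not run | as for the eight |

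The two columns of figures agree: a shortfall s gives an error of 2[1 − Φ(1.96(1 − s))], which is 6.3% at s = 5%, 7.8% at 10% and 10.0% at 16%.

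Three qualifications:

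- In set A, selecting covariates before period enters gives a shortfall of only 0.8-9.5%, but at rate ratio 0.5 it biases the log-ratio towards the null by 0.04 to 0.06.
- In set A, selection itself accounts for about 7 to 13 points of the shortfall. The rest is small-sample error of maximum likelihood fitting.
- In set B, forcing without stepwise leaves the SE within about 1% of the truth, so forcing is not the cause of the narrow interval.

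**Four fits.** Comparing all 86 with 74 random completers under stepwise plus forcing, the SD of the difference in period log-ratio is 0.071-0.077 with a common covariate set and 0.095-0.102 if selection is rerun. The set changes in 82-85% of trials.

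**One site.** With a single site the random effect adds the same quantity to every patient, so it is aliased with the intercept. A REML check on the days scale gave log-likelihood −127.29 at site variance 0, 1, 10 and 100, with the period estimate (−2.159) and SE (0.647) unchanged.

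**Definitions.** SAP 6.2.4.1 counts connective tissue disease as immunocompromising; SAP Appendix B omits it.

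**The case against.** The strongest reply has five parts.

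1. **The percentages are not in the documents.** They rest on assumed effects, and the selection order is unknown because the procedure name is redacted. This stands, so the figures must be labelled as simulation results.

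2. **Forcing is part of the plan and repairs much of the problem.** This stands: the shortfall falls to roughly 5-9%. The direction remains, and the rule for forcing is unstated.

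3. **A fixed list can do worse.** In scenario (d) the eight alone left a log-ratio bias of −0.069, against −0.007 for stepwise with forcing, and error of 7.1% against 6.9%. With maximum likelihood dispersion in (d) the gain disappears (9.0% against 9.2%, 400 trials). Both points stand and shape the fix: the list must cover the plausible confounders, and the dispersion estimator must be named.

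4. **Little changes at the design effect.** The unadjusted log-ratio SE is √[(1/4 + 0.3125 + 1/2 + 0.3125)/43] = 0.179, so z = 0.693/0.179 = 3.9. With shortfalls of 9% and 16%, z is still 3.5 and 3.3. True; the issue bites for smaller or borderline effects.

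5. **The site term is harmless and the SAP allows some flexibility.** SAP 6.0 permits modifying infeasible analyses, and 6.2.4.1 allows categories to be merged, so the df count is an upper figure. The text on the four fits may mean one common model, and the table shells are not available to check. All fair; these are reasons to tidy the text.

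A reader might infer that the site term distorts the period effect, or that it will cause a failed fit and so a change of distribution. The documents support neither: the estimate and SE do not move, and no failed fit has been shown.

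**Conclusion.** The point holds for the secondary adjusted model only. With period kept in the model, the reported SE is roughly 10-16% too small under stepwise alone (actual error about 8-11%) and roughly 5-9% too small with imbalance forcing (about 6-8%). If covariates were selected before period entered, the shortfall could be as low as about 1%.

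These sizes depend on assumed prevalences, prognostic strengths and imbalances. Kenward-Roger itself was not simulated. The direction was the same in all three sets.

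Two stronger readings should be resisted. The primary t-test involves no selection, so nothing here weakens it. And no fixed percentage can be read off the plan, because the documents give no covariate effects and redact the procedure.

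That the site variance cannot be estimated, and that the two immunocompromised definitions differ, follow from the text and need no simulation.

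**What to change.** In SAP 6.2.4.1, before outcome data are analysed:

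- Replace stepwise selection with a covariate set chosen on clinical grounds from the listed variables, kept regardless of p-value and used in all four fits. Settle the merging of categories at the same time.
- Make the list cover the plausible confounders. Keeping all 13 distinct candidates is workable. A shorter example is age, Charlson index, infection type, lesion area, SIRS, recurrence, prior antibiotic failure and insurance type (12 df, 86/12 = 7.2 patients per df).
- If a shorter list is used, add a sensitivity fit that brings in other listed covariates by a stated imbalance rule, for example pre/post p<0.1. In scenario (d) this cut the bias from −0.069 to −0.021 and the error from 7.1% to 4.6%.
- Name the dispersion estimator and use t on residual df. With maximum likelihood dispersion the eight gave errors of 8.1% in (b) and 9.9% in (d), against 5.4% and 7.1% with moment dispersion.
- Delete the RANDOM site term and the between-site independence sentence, list health resource use once, and reconcile the immunocompromised definition with Appendix B.

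**Cost.** SAP wording and simpler code. With about eight covariates the reported SE is roughly 4-10% larger, mainly the correct width: against stepwise with forcing it was 0.165-0.179 versus 0.158-0.172, while the actual SD was 0.169-0.184 versus 0.173-0.186. Some confounding remains if a short list omits a main confounder.

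Keeping every candidate costs more. In set A with no prognostic covariates, the scaled SE was 0.1921 × (1 − 0.041) = 0.184, against 0.1761 × (1 − 0.108) = 0.157 for stepwise, or 17% larger. The actual SD rose by 9% (0.1921/0.1761), so part of that width is a real loss of precision.
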